BMS-936558

SYNOPSIS

Clinical Protocol CA209064

Protocol Title: CA209-064: An Open-Label, Randomized, Phase 2 Study of Nivolumab Given Sequentially with Ipilimumab in Subjects with Advanced or Metastatic Melanoma (CheckMate 064: CHECKpoint pathway and nivoluMAb clinical Trial Evaluation 064)

Investigational Product(s), Dose and Mode of Administration, Duration of Treatment with Investigational Product(s): Nivolumab (BMS-936558) at 3 mg/kg every 2 weeks for up to 6 doses in Induction Period. Ipilimumab at 3 mg/kg every 3 weeks for up to 4 doses in Induction Period. Nivolumab at 3 mg/kg every 2 weeks in Continuation Period until progression, unacceptable toxicity, or withdrawal of consent, for a maximum duration of 2 years from first study treatment in Induction Period 1.

Study Phase: 2

Objectives:

Primary Objective:

 To evaluate the incidence of treatment-related Grade 3 - 5 AEs during the Induction Period in subjects receiving sequential induction treatment with either nivolumab followed by ipilimumab or ipilimumab followed by nivolumab

Secondary Objectives:

- To evaluate the response rate at Week 25 in subjects receiving sequential induction treatment with either nivolumab followed by ipilimumab or ipilimumab followed by nivolumab
- To evaluate progression rates at Week 13 and Week 25 in subjects receiving sequential induction treatment with either nivolumab followed by ipilimumab or ipilimumab followed by nivolumab

[figure not shown]
Study Design:

This is an open-label, randomized, Phase 2 study of two schedules of nivolumab given sequentially with ipilimumab, in adult (\geq 18 years old) male and female subjects with advanced (unresectable Stage III) or metastatic (Stage IV) melanoma. Approximately 80 subjects will be randomized (1:1) to receive one of two dosing schedules (Cohort A or B). Randomization will stay open until at least 40 subjects in each Cohort have been treated with at least one dose of study treatment in Induction Period 1 and 35 subjects in each Cohort have received at least one dose of study treatment in Induction Period 2.

Subjects may be treatment-naive or have experienced disease recurrence or progression after one prior systemic therapy (prior immunotherapy with anti-PD1 or anti-CTLA-4 is prohibited). The two dosing schedules to be explored are presented in Figure 1.

Accrual duration is expected to be around 1 year. Primary and secondary endpoint analysis will be performed when at least 40 subjects per cohort have completed/discontinued Induction Period 1 and at least 35 subjects per cohort have completed/discontinued Induction Period 2, and all treated subjects with an objective response at Week 25 have been followed through study Week 33 in order to confirm disease response. This will take place after a maximum of 32 weeks after last patient first treatment date. An update of OS analysis is planned after 65% of the subjects have died or 2 years of follow-up time from last subject randomized, whichever comes first. Assuming a median OS of 20 months for both cohorts, approximately 65% of the subjects would have died after a 12 months accrual period followed by a two years of follow-up time.

Figure 1: Study Design Schematic

Study Population:

Key Inclusion Criteria:

- Subjects with histologically confirmed unresectable Stage III or Stage IV melanoma
- Subjects may be treatment-naive, or have experienced disease recurrence or progression during or after one prior systemic regimen for advanced disease
- Subjects must have measurable disease by CT or MRI per RECIST 1.1 criteria. (radiographic tumor assessment must be performed within 28 days prior to randomization.)
- Eastern Cooperative Oncology Group (ECOG) performance status of 0 or 1 (refer to Appendix 1)
- Subjects with known BRAF V600 mutation status or consent to BRAF V600 mutation testing per local
 institutional standards during the Screening Period, the results of which must be reported within 3 months of
 randomization
- Subjects must have sufficient tumor tissue accessible for baseline and post-treatment biopsies (core needle or excisional). The site of tumor biopsy should not be the only site of measurable disease.

Key Exclusion Criteria:

- Subjects with active CNS metastases are excluded. Subjects are eligible if CNS metastases are adequately
 treated with surgery and/or radiation therapy, and subjects are neurologically returned to baseline (except for
 residual signs or symptoms related to the CNS treatment) and neurologically and radiographically stable for at
 least 6 weeks prior to enrollment. In addition, subjects must be either off corticosteroids, or on a stable or
 decreasing dose of ≤ 10 mg daily prednisone (or equivalent) for at least 14 days prior to study treatment.
- Subjects with carcinomatous meningitis

- Subjects with active, known or suspected autoimmune disease. Subjects with vitiligo, type I diabetes mellitus, residual hypothyroidism due to autoimmune thyroiditis only requiring hormone replacement, or conditions not expected to recur in the absence of an external trigger are permitted to enroll.
- Subjects with a condition requiring systemic treatment with either corticosteroids (> 10 mg daily prednisone equivalent) or other immunosuppressive medications within 14 days of randomization. Inhaled or topical steroids, and adrenal replacement steroid doses > 10 mg daily prednisone equivalent, are permitted in the absence of active autoimmune disease
- Prior therapy with anti-PD-1, anti-PD-L1, anti-PD-L2, anti-CD137, or anti-CTLA-4 antibody (including ipilimumab or any other antibody or drug specifically targeting T-cell co-stimulation or checkpoint pathways).
- Subjects who received prior treatment with other immunotherapies (eg, antibodies, vaccines, adoptive T-cell transfer), must have experienced disease progression at least 6 weeks prior to first dose of study treatment and, with the exception of IL-2 or adjuvant interferon, must be discussed and approved by the Medical Monitor prior to signing informed consent
- Prior therapy with BRAF inhibitor (eg, vemurafenib)

Study Assessments & Endpoints: The primary endpoint of the study is the rate of treatment-related Grade 3-5 AEs during the Induction Period (Periods 1 and 2) in subjects receiving sequential induction treatment with either nivolumab followed by ipilimumab or ipilimumab followed by nivolumab.

The treatment-related Grade 3 - 5 AEs rate is defined as number of subjects who experienced at least 1 treatment related Grade3 - 5 adverse event (per NCI CTCAE v 4.0 criteria, any PT terms) with an onset date after or on first day of the induction period and not later than discontinuation date from the Induction Period, divided by number of treated subjects. AEs with an onset date after start of subsequent anti-cancer therapy, or start date of Continuation Period treatment will not be included. For subjects who discontinue Induction Period early and enter the Follow-Up Period, AEs that occur in Follow-Up, including those before Week 25, will not be included in the primary endpoint. For subjects who discontinue treatment before the end of Induction Period 1 or 2 but who are eligible to enter the next study period, AEs that occur before end of Induction Period 2 will be included in the primary endpoint, even if they occur after dosing ends while they are waiting to enter the next study period.

The secondary endpoints are Response Rate at Week 25 and Progression Rates at Weeks 13 and 25. Subjects will be assessed for response via tumor assessments (CT or MRI) prior to dosing at Weeks 13, 25, 33, 41, 49 (+/- 1 weeks) and then every 12 weeks. Response rate at Week 25 is defined as the number of subjects who have a complete response (CR) or partial response (PR) at Week 25 (regardless of the tumor assessment at Week 13), with confirmation at scheduled scan at Week 33, divided by the total number of randomized subjects. Progression rates at Weeks 13 and 25 are defined as the number of subjects who have Progressive Disease (PD) per RECIST 1.1 at the specific timepoint (Week 13 or Week 25) divided by the total number of randomized subjects.

Statistical Considerations:

Sample Size: This trial is an estimation trial. Sample size in this study will be approximately 40 subjects per cohort and is not based on power considerations. Tables below provide the 95% confidence intervals computed from different observed rates. Those tables indicate what would be the reliability of the AE rate estimates for N=40 (Table 8.1-1) and N=35 (Table 8.1-2) treated subjects. A threshold of 45% will be applied to the upper limit of the confidence interval as an informal guideline for high toxicity

Thirty-five subjects per cohort will be the minimum number of subjects receiving treatment in Induction Period 2. For that purpose, randomization will stay open until at least 40 subjects in each cohort have been treated with at least one dose of study treatment in Induction Period 1 and 35 subjects in each cohort have received at least one dose of study treatment in Induction Period 2. Assuming a drop-out rate during induction period 1 would be at most 12.5%, at least 35 subjects would be treated in induction period 2 if 40 subjects are to be randomized per cohort.

Revised Protocol No.: 01

Analyses:

Primary analysis:

Rate of treatment-related Grade 3-5 AEs during the induction period will be computed by treatment cohort using all treated subjects. Corresponding 95% CIs will be calculated using the Clopper-Pearson method. As sensitivity analysis, rates and 95% CI will be also computed using the subset of subjects who received at least one dose of study treatment in Induction Period 2.

Secondary analyses:

Response rate at Week 25 will be computed by treatment arm using all randomized subjects. Response rate estimates and corresponding 95% CIs will be calculated using the Clopper-Pearson method. Response rates including only those subjects who had a tumor assessment at Week 25 will also be computed. Duration of response from Week 25 will be assessed for subjects with confirmed response at Week 25. Median DOR estimate and corresponding 95% CIs will be provided for each sequential induction regimen using the Kaplan-Meier methodology. Progression rate estimates at Week 13 and Week 25 along with corresponding 95% CIs will be calculated using the Clopper-Pearson method.

TABLE OF CONTENTS

TITLE PAGE	J
DOCUMENT HISTORY	3
SYNOPSIS	4
TABLE OF CONTENTS	8
1 INTRODUCTION	13
1.3 Objective(s)	17
1.3.1 Primary Objective	17
1.3.2 Secondary Objectives	17
	2.5
2 ETHICAL CONSIDERATIONS	27
2.1 Good Clinical Practice	27
2.2 Institutional Review Board/Independent Ethics Committee	27
2.3 Informed Consent	27
3 INVESTIGATIONAL PLAN	28
3.1 Study Design and Duration	28
3.1.1 Screening	30

1.3 Objective(s)

1.3.1 Primary Objective

 To evaluate the incidence of treatment-related Grade 3-5 AEs during the Induction Period in subjects receiving sequential induction treatment with either nivolumab followed by ipilimumab or ipiliumuab followed by nivolumab

1.3.2 Secondary Objectives

- To evaluate the response rate at Week 25 in subjects receiving sequential induction treatment with either nivolumab followed by ipilimumab or ipilimumab followed by nivolumab
- To evaluate progression rates at Week 13 and Week 25 in subjects receiving sequential induction treatment with either nivolumab followed by pillimumab or ipilimumab followed by nivolumab

2 ETHICAL CONSIDERATIONS

2.1 Good Clinical Practice

This study will be conducted in accordance with Good Clinical Practice (GCP), as defined by the International Conference on Harmonisation (ICH) and in accordance with the ethical principles underlying European Union Directive 2001/20/EC and the United States Code of Federal Regulations, Title 21, Part 50 (21CFR50).

The study will be conducted in compliance with the protocol. The protocol and any amendments and the subject informed consent will receive Institutional Review Board/Independent Ethics Committee (IRB/IEC) approval/favorable opinion prior to initiation of the study.

All potential serious breaches must be reported to BMS immediately. A serious breach is a breach of the conditions and principles of GCP in connection with the study or the protocol, which is likely to affect, to a significant degree, the safety or physical or mental integrity of the subjects of the study or the scientific value of the study.

Personnel involved in conducting this study will be qualified by education, training, and experience to perform their respective tasks.

This study will not use the services of study personnel where sanctions have been invoked or where there has been scientific misconduct or fraud (eg, loss of medical licensure, debarment).

2.2 Institutional Review Board/Independent Ethics Committee

Before study initiation, the investigator must have written and dated approval/favorable opinion from the IRB/IEC for the protocol, consent form, subject recruitment materials (eg, advertisements), and any other written information to be provided to subjects. The investigator or BMS should also provide the IRB/IEC with a copy of the Investigator Brochure or product labeling information to be provided to subjects and any updates.

The investigator or BMS should provide the IRB/IEC with reports, updates and other information (eg, expedited safety reports, amendments, and administrative letters) according to regulatory requirements or institution procedures.

2.3 Informed Consent

Investigators must ensure that subjects are clearly and fully informed about the purpose, potential risks, and other critical issues regarding clinical studies in which they volunteer to participate.

In situations where consent cannot be given to subjects, their legally acceptable representatives are clearly and fully informed about the purpose, potential risks, and other critical issues regarding clinical studies in which the subject volunteers to participate.

BMS will provide the investigator with an appropriate (ie, Global or Local) sample informed consent form which will include all elements required by ICH, GCP and applicable regulatory requirements. The sample informed consent form will adhere to the ethical principles that have their origin in the Declaration of Helsinki.

Investigators must:

- Provide a copy of the consent form and written information about the study in the language in which the subject is most proficient prior to clinical study participation. The language must be non-technical and easily understood.
- Allow time necessary for subject or subject's legally acceptable representative to inquire about the details of the study.
- Obtain an informed consent signed and personally dated by the subject or the subject's legally acceptable representative and by the person who conducted the informed consent discussion
- Obtain the IRB/IEC's written approval/favorable opinion of the written informed consent form and any other information to be provided to the subjects, prior to the beginning of the study, and after any revisions are completed for new information.
- If informed consent is initially given by a subject's legally acceptable representative or legal guardian, and the subject subsequently becomes capable of making and communicating his or her informed consent during the study, consent must additionally be obtained from the subject.
- Revise the informed consent whenever important new information becomes available that is
 relevant to the subject's consent. The investigator, or a person designated by the investigator,
 should fully inform the subject or the subject's legally acceptable representative or legal
 guardian, of all pertinent aspects of the study and of any new information relevant to the
 subject's willingness to continue participation in the study. This communication should be
 documented.

The confidentiality of records that could identify subjects must be protected, respecting the privacy and confidentiality rules applicable to regulatory requirements, the subjects' signed ICF and, in the US, the subjects' signed HIPAA Authorization.

The consent form must also include a statement that BMS and regulatory authorities have direct access to subject records.

The rights, safety, and well-being of the study subjects are the most important considerations and should prevail over interests of science and society.

3 INVESTIGATIONAL PLAN

[figure not shown]
3.1 Study Design and Duration

This is an open-label, randomized Phase 2 study of two schedules of nivolumab given sequentially with ipilimumab, in adult (≥ 18 years old) male and female subjects with advanced (unresectable Stage III) or metastatic (Stage IV) melanoma. Approximately 80 subjects will be randomized (1:1) to receive one of two dosing schedules (Cohort A or B).

Randomization will stay open until at least 40 subjects in each Cohort have been treated with at least one dose of study treatment in Induction Period 1 and 35 subjects in each Cohort have received at least one dose of study treatment in Induction Period 2.

Subjects may be treatment-naive or have experienced disease recurrence or progression after one prior systemic therapy (prior immunotherapy with anti-PD1 or anti-CTLA-4 is prohibited). The two dosing schedules to be explored are presented in Figure 3.1-1.

Subjects in Cohort A will receive nivolumab at 3 mg/kg every 2 weeks for up to 6 doses during Weeks 1 to 13 in Induction Period 1, followed by ipilimumab at 3 mg/kg every 3 weeks for up to 4 doses during Weeks 13 to 25 in Induction Period 2. Subjects in Cohort B will receive the reciprocal sequence.

During Induction Periods 1 and 2, doses of either nivolumab or ipilimumab may be omitted if there is an AE which precludes treatment at a scheduled treatment visit (Section 4.3.4.1). Dose delays, reductions, and escalations are not permitted for either nivolumab or ipilimumab. Dose interruptions will be allowed for infusion reactions, according to guidelines in Section 4.3.4. After completion of Induction Period 2, eligible subjects in both cohorts will enter the Continuation Period and receive nivolumab at 3 mg/kg every 2 weeks until progression, unacceptable toxicity, or withdrawal of consent. The maximum duration of treatment to be administered to an individual subject in this study is 2 years from the first study treatment in Induction Period 1. Additional ipilimumab treatment during the Continuation Period will not be allowed.

Tumor assessments will be obtained prior to dosing, as applicable, at the targeted weeks (Table 5.1-1, Table 5.1-2, Table 5.1-3, Table 5.1-4, Table 5.1-5). Tumor response will be evaluated at the end of Induction Period 1 (Week 13) and at the end of Induction Period 2 (Week 25), then Week 33 and Week 41, and then every 12 weeks starting at Week 49, using RECIST version 1.1. Before treatment in the Continuation Period can begin, the tumor assessment at the end of

Induction Period 2 must be reviewed to determine if the subject meets any of the exception criteria in Section 3.1.2.3. During the Continuation Period, each tumor assessment must be reviewed before the next dose of nivolumab can be given.

In the Continuation Period, subjects will be permitted to continue nivolumab treatment beyond initial RECIST 1.1-defined progression if they are assessed by the investigator to be deriving clinical benefit, are tolerating study treatment, and provide informed consent (see Section 4.3.5). Such subjects should discontinue study treatment upon evidence of further progression.

This study will consist of 3 phases: Screening, Treatment (Induction Period 1, Induction Period 2, and Continuation Period), and Follow-Up.

3.1.1 Screening

- Begins by establishing subject's initial eligibility and signing of the informed consent.).
- Subject is enrolled using the Interactive Voice Response System (IVRS). This study permits the re-enrollment of a subject that has discontinued the study as a pre-treatment failure (ie, subject has not been randomized / has not been treated). If re-enrolled, the subject must be re-consented.
- Subject is assessed for complete study eligibility within 28 days prior to randomization (Table 5.1-1).
- Subjects meeting all eligibility criteria must undergo a fresh tumor biopsy (Section 5.6.1), ECG, and whole blood collection for SNP assessment.

3.1.2 Treatment Phase (Induction Period 1, Induction Period 2, Continuation Period)

- Begins with the randomization call to the IVRS. The subject is randomly assigned to either Cohort A or Cohort B.
- Doses of either nivolumab or ipilimumab may be omitted if there is an AE which precludes treatment at a scheduled treatment visit (Section 4.3.4.1). Treatment may resume at the next scheduled dose if retreatment criteria (specified in Section 4.3.4.2) are met.
- Dose interruptions will be allowed for infusion reactions, according to guidelines in Section 4.3.4.3.
- Tumor biopsies (Section 5.6.1) must be performed at Week 13 and time of disease progression, unless the designated lesion(s) have responded during study treatment and are no longer accessible for biopsy.
- Treatment Phase ends when subject completes or discontinues all study dosing.

3.1.2.1 Induction Period 1

• Induction Period 1 begins at Week 1, Day 1. Induction Period 1 is the first 12 weeks of study treatment (Week 1 to Week 13). Subjects must receive the first dose of study treatment within 3 working days following randomization.

- Subjects in Cohort A will receive nivolumab at a dose of 3 mg/kg as a 60 minute IV infusion every 2 weeks (14 days) for up to 6 doses.
- Subjects in Cohort B will receive ipilimumab at a dose of 3 mg/kg as a 90 minute IV infusion every 3 weeks (21 days) for up to 4 doses.
- Study assessments will be conducted as outlined in Table 5.1-2 and Table 5.1-3.
- Tumor biopsies (Section 5.6.1) must be performed prior to dosing at Week 13, unless the designated lesion(s) have responded during study treatment and are no longer accessible for biopsy.
- All subjects must have tumor assessment performed at Week 13 (prior to the first dose in Induction Period 2). This includes any subject who may have discontinued treatment prior to receiving all planned Induction Period 1 doses.
- Subjects who have clinical or radiographic progressive disease prior to the completion of Induction Period 1 are to remain on their current study treatment for the remainder of Induction Period 1, provided they are tolerating study treatment and do not have rapid clinical deterioration.
- Subjects who do not receive all planned doses in Induction Period 1, including those who discontinue Induction Period 1 treatment early due to progression or discontinuation criteria (Section 4.3.6.2), are to continue their scheduled study assessments (as per Table 5.1-2 and Table 5.1-3) and are still eligible to receive the alternative treatment in Induction Period 2, starting at Week 13.
- After completion of Induction Period 1, subjects will proceed to Induction Period 2, regardless of the results of the tumor assessment at the end of Induction Period 1.

3.1.2.2 Induction Period 2

- Induction Period 2 begins at Week 13 and continues to Week 25.
 - Subjects in Cohort A will receive ipilimumab at a dose of 3 mg/kg as a 90 minute IV infusion every 3 weeks (21 days) for up to 4 doses.
 - Subjects in Cohort B will receive nivolumab at a dose of 3 mg/kg as a 60 minute IV infusion every 2 weeks (14 days) for up to 6 doses.
- Subjects with drug-related AEs after the last dose in Induction Period 1 who fail to meet retreatment criteria (Section 4.3.4.2) at Week 13 will still begin Induction Period 2 at Week 13 and require omission of the initial dose(s) in Induction Period 2 until retreatment criteria are met.
- Study assessments will be conducted as outlined in Table 5.1-2 and Table 5.1-3.
- All subjects, including those who discontinue study treatment prior to receiving all planned doses during Induction Period 2, must have a tumor assessment at Week 25 (after the last dose of Induction Period 2 and prior to the first dose of the Continuation Period).
- Subjects who have clinical or radiographic progressive disease prior to the completion of Induction Period 2 are to remain on their current study treatment for the remainder of Induction Period 2, provided they are tolerating study treatment and do not have rapid clinical deterioration

• Subjects who do not receive all planned treatment doses in Induction Period 2, including those who discontinue Induction Period 2 treatment early due to progression or discontinuation criteria in Section 4.3.6.2, are to continue their scheduled study assessments (as per Table 5.1-2 and Table 5.1-3) and may still be eligible to receive treatment in the Continuation Period, starting at Week 25.

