4.3 Selection and Timing of Dose for Each Subject

Dosing calculations should be based on the body weight assessed at each visit as per Table 5.1-2, Table 5.1-3, and Table 5.1-4. All doses should be rounded to the nearest milligram. There will be no nivolumab or ipilimumab dose escalations or reductions permitted.

The first dose of study drug will be administered on Week 1, Day 1. Subsequent doses are to be scheduled from the calendar date of the first dose and have a +/- 3 day dosing window. Please refer to Table 5.1-2 and Table 5.1-3 for the appropriate timing of doses (in terms of number of Weeks/Days from first dose) in the Induction Period.

After each nivolumab dose, the next dose of study treatment may be given no sooner than 12 days later. After each ipilimumab dose, the next dose of study treatment may be given no sooner than 19 days later.

There are no premedications recommended for nivolumab or ipilimumab. Subjects should be carefully monitored for infusion reactions during nivolumab and ipilimumab administration. If an infusion reaction is noted, subjects should be managed according to Section 4.3.4.3.

There will be no dose delays permitted in this study. Doses of nivolumab or ipilimumab will be omitted if omission criteria, described in Section 4.3.4.1, are met. Treatment may resume at the next scheduled dose if retreatment criteria (specified in Section 4.3.4.2) are met.

The maximum duration of study treatment to be administered to an invididual subject is 2 years from the first study treatment in Induction Period 1.

4.3.1 Induction Period 1

Induction Period 1 will be the first 12 weeks of study treatment (Weeks 1 to 13).

• Subjects in Cohort A will receive nivolumab at a dose of 3 mg/kg as a 60 minute IV infusion every 2 weeks (14 days) for up to 6 doses.

• Subjects in Cohort B will receive ipilimumab at a dose of 3 mg/kg as a 90 minute IV infusion every 3 weeks (21 days) for up to 4 doses.

4.3.2 Induction Period 2

After completion of Induction Period 1, subjects will proceed to Induction Period 2 (12 weeks duration, from Week 13 to 25), regardless of the results of the tumor assessment at the end of Induction Period 1.

- Subjects in Cohort A will receive ipilimumab at a dose of 3 mg/kg as a 90 minute IV infusion every 3 weeks (21 days) for up to 4 doses.
- Subjects in Cohort B will receive nivolumab at a dose of 3 mg/kg as a 60 minute IV infusion every 2 weeks (14 days) for up to 6 doses.

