4.3.4.1 Dose Omissions for Nivolumab or Ipilimumab

Doses of nivolumab or ipilimumab should be omitted (not delayed) if any of the following criteria are met:

- Any Grade 2 non-skin, drug-related adverse event, with the following exceptions:
 - Grade 2 drug-related fatigue or laboratory abnormalities do not require dose omission
- Any Grade 3 skin, drug-related adverse event
- Any Grade 3 drug-related laboratory abnormality, with the following exceptions for lymphopenia, leukopenia, AST, ALT, or total bilirubin:
 - Grade 3 lymphopenia or leukopenia does not require dose omission
 - If a subject has baseline AST, ALT, or total bilirubin that is within normal limits, omit dosing for drug-related Grade ≥ 2 toxicity
 - If a subject has baseline AST, ALT, or total bilirubin within the Grade 1 toxicity range, omit dosing for drug-related Grade ≥ 3 toxicity
- Any adverse event, laboratory abnormality, or intercurrent illness which, in the judgment of the investigator, warrants omitting the dose of study medication

If the criteria to resume treatment (specified in Section 4.3.4.3) are met within the dosing window (Week $X \pm 3$ days), then the dose may be given.

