4.3.4.2 Criteria to Resume Treatment with Nivolumab or Ipilimumab

Subjects may resume treatment with nivolumab or ipilimumab when the drug-related AE(s) resolve to Grade ≤ 1 or baseline value, with the following exceptions:

• Subjects may resume treatment in the presence of Grade 2 fatigue

• Subjects who have not experienced a Grade 3 drug-related skin AE may resume treatment in the presence of Grade 2 skin toxicity

- Subjects with baseline AST/ALT or total bilirubin in the Grade 1 toxicity range who require dose omissions for reasons other than a 2-grade shift in AST/ALT or total bilirubin may resume treatment in the presence of Grade 2 AST/ALT or total bilirubin
- Drug-related pulmonary toxicity, diarrhea, or colitis must have resolved to baseline before treatment is resumed
- Drug-related endocrinopathies adequately controlled with only physiologic hormone replacement may resume treatment

If dosing is interrupted > 6 weeks, the subject must be permanently discontinued from study treatment with that particular drug, except as specified in Section 4.3.6.2.

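### Sections 3.1.2.2 and 4.3.4.1 disagree on whether certain laboratory AEs require omission of the first Induction Period 2 dose, and the protocol does not say which rule prevails

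*Protocol*

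**What the plan says.** Four parts of the protocol bear on the first Induction Period 2 dose.

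- **General rule (Sections 3.1 and 4.3).** Section 4.3 states: "Doses of nivolumab or ipilimumab will be omitted if omission criteria, described in Section 4.3.4.1, are met". Section 3.1 refers to the same omission section for both Induction Periods. Neither sets Week 13 apart.
- **Omission criteria (Section 4.3.4.1).** Two exemptions matter here: "Grade 2 drug-related fatigue or laboratory abnormalities do not require dose omission" and "Grade 3 lymphopenia or leukopenia does not require dose omission". The first does not reach AST, ALT or total bilirubin with a normal baseline, which have their own rule and are omitted from Grade 2 upward.
- **Week 13 rule (Section 3.1.2.2).** It concerns subjects with drug-related AEs following their final Period 1 dose, "who fail to meet retreatment criteria (Section 4.3.4.2) at Week 13 will still begin Induction Period 2 at Week 13". The sentence goes on to say that they "require omission of the initial dose(s) in Induction Period 2 until retreatment criteria are met".
- **Resumption criteria (Section 4.3.4.2).** The threshold is: "Subjects may resume treatment with nivolumab or ipilimumab when the drug-related AE(s) resolve to Grade ≤ 1 or baseline value". The relaxations cover Grade 2 fatigue, Grade 2 skin toxicity without an earlier Grade 3 skin AE, Grade 2 liver tests with a Grade 1 baseline, and endocrinopathy controlled by hormone replacement. Pulmonary toxicity, diarrhea and colitis must be back to baseline.

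The cross-references do not settle the matter. Sections 4.3.4.1 and 4.3.6.2 both point to Section 4.3.4.3 for the resumption criteria, but 4.3.4.3 deals with infusion reactions. In 4.3.6.2 that pointer governs the start of the alternative agent at Week 13 in subjects who discontinued the first drug.

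**The concern.** Section 3.1.2.2 takes a test written for restarting after an omission and applies it to a dose of a drug that has not yet been given. It does so whether or not the subject ever met an omission criterion. The exemptions in Section 4.3.4.1 for lymphopenia, leukopenia and Grade 2 laboratory abnormalities have no counterpart in Section 4.3.4.2. A subject can therefore reach Week 13 with an AE that one section says is no reason to omit and another says is.

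Week 13 is the crossover that defines the sequences being compared. Two sites could read the rule differently in good faith, so the Period 2 treatment actually given could vary by site for reasons unrelated to the randomized sequence. The trial is open-label, and the two cohorts lose different fractions of planned treatment from one omission.

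**Working it through.** The protocol gives no figure for this point to reproduce. The check is a comparison of rules, with a short calculation of what one omission costs.

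**Case comparison.** Take a subject at Week 13 with a drug-related AE following the last Period 1 dose, Grade 0 at baseline unless stated, no earlier omission, and the investigator-judgment item of Section 4.3.4.1 not invoked.

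| AE at Week 13 | Section 4.3.4.1 | Sections 3.1.2.2 and 4.3.4.2 | Result |
|---|---|---|---|
| Grade 3 lymphopenia or leukopenia | omission not required | omission required | conflict |
| Grade 2 laboratory AE other than AST, ALT, bilirubin | omission not required | omission required | conflict |
| Grade 2 AST, ALT or bilirubin, normal baseline | omit | omission required | agree |
| Grade 2 fatigue | omission not required | dose allowed | agree |
| Grade 2 skin AE, no earlier Grade 3 skin AE | omission not required | dose allowed | agree |
| Grade 1 diarrhea | no trigger listed | not back to baseline: omission required | differ |

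The point rests on the first two rows, where an explicit exemption meets an explicit requirement. In the last row the sections also part, but 4.3.4.1 is silent there and grants no exemption.

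**Is a dose at stake?** Section 4.3 permits no delays. Section 4.3.4.1 lets the dose be given only if the criteria are met within 3 days either side of the scheduled date. Beyond that the dose is lost. Tables 5.1-2 and 5.1-3 schedule chemistry and hematology at Week 13 in both cohorts, and Section 5.3.5 places them within 72 hours before dosing, so a site will have the results in hand when it decides.

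**Cost of one omission**, from the planned doses in Section 3.1.2.2:

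- Cohort A, ipilimumab: 1 / 4 = 25% of planned Period 2 doses.
- Cohort B, nivolumab: 1 / 6 = 16.7% of planned Period 2 doses.

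**How many subjects?** This cannot be derived. Section 6.3 sends a laboratory result to the AE page only if it is clinically significant or meets the SAE definition, led to stopping or interrupting study drug, or needed specific corrective therapy. Section 3.1.2.2 may also be read as covering only AEs that began after the last Period 1 dose. Both limits shrink the group without emptying it.

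**Which analyses does it touch?** Period 2 exposure is affected directly. Membership of the Period 2 sensitivity subset (Section 8.4.2) and of the Period 2 safety denominator (Section 8.4.4) changes only if a subject ends up with no Period 2 dose at all. That takes omission of all 4 or all 6 doses, not just the first.

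**The case against.** The strongest reply is that both rules can be obeyed at once. Section 4.3 says when doses are omitted, not that they are omitted only then. An exemption from one trigger is not an instruction to dose. On that reading Section 3.1.2.2 is a specific, stricter rule for entering Period 2, and it controls. There is some support: Section 4.3.6.2 also uses resumption criteria at the Week 13 and Week 25 boundaries, for subjects who stopped the earlier drug, and Section 4.3.4 notes that AEs from Period 2 onward may relate to either drug or both.

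This reading is possible, but no section states it. A site working from Section 4.3 and the omission criteria would find no reason to withhold the dose and no pointer to a stricter Week 13 rule. The two mistaken cross-references make a wrong turn more likely.

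Part of the objection stands in full. A threshold for resuming that is stricter than the threshold for omitting is not an error once a dose has been omitted, so ordinary resumption within a period is not at issue. The objection is also right that the affected group is narrow.

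Nor can it be said that laboratory findings fall outside the AE rules. Section 6 includes abnormal laboratory findings in its AE definition, and both dosing sections list laboratory values among their exceptions.

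**Conclusion.** The contradiction is real and worth correcting. For drug-related Grade 3 lymphopenia or leukopenia, and for Grade 2 laboratory AEs outside the AST, ALT and bilirubin rule, the protocol both requires and does not require omission of the first Period 2 dose, with no order of precedence. Its size is 25% of planned ipilimumab doses in Cohort A or 16.7% of planned nivolumab doses in Cohort B per omission, in an unknown but probably small number of subjects. The conclusion assumes that such results are recorded as drug-related AEs and that sites may differ in which section they follow.

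A reader might infer more than the protocol supports:

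- **That the primary rate shifts.** No direct effect is shown. A subject with treatment-related Grade 3 lymphopenia recorded during induction is already in the numerator, and the denominator is all treated subjects. For Grade 2 laboratory AEs, nothing links the Week 13 decision to a later Grade 3-5 event. It does not follow that the informal 45% guideline would be crossed.
- **That the planned drop-out margin is used up.** The 12.5% in Section 8.1 is an assumption, not a quota. Randomization stays open until 35 subjects per cohort have had a Period 2 dose, so a shortfall would prolong enrollment.
- **That the six-week limit forces discontinuation.** Section 4.3.6.2 limits interruptions of a particular drug. Whether a drug not yet started can be interrupted is not stated.

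**What to change.** Reconcile Sections 3.1.2.2, 4.3, 4.3.4.1 and 4.3.4.2 so that one stated set of criteria governs the first Induction Period 2 dose. Correct the references to Section 4.3.4.3 in Sections 4.3.4.1 and 4.3.6.2 at the same time. If Section 3.1.2.2 is meant to override the general omission criteria at Week 13, say so in both places; if not, align it with them. Which set applies is a clinical decision for the sponsor's clinical team, and this review takes no position on it.

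For the analysis, add one flag to the exposure data marking any first Period 2 dose omitted only because of an AE that Section 4.3.4.1 exempts, and report the count by cohort. That would show whether the ambiguity mattered in practice.

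The cost is a clarifying amendment or administrative letter and one derived variable. No extra subjects, visits or procedures are needed.
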